#### 12.0 DISCIPLINE REVIEW

This study will not utilize discipline review.

#### 13.0 REGISTRATION GUIDELINES

#### 13.1 Registration Timing

Patients must be registered prior to initiation of treatment (no more than 5 working days prior to planned start of treatment).

13.2 Investigator/Site Registration

Prior to the recruitment of a patient for this study, investigators must be registered members of a Cooperative Group. Each investigator must have an NCI investigator number and must maintain an "active" investigator registration status through the annual submission of a complete investigator registration packet to CTEP.

a. CTEP Investigator Registration Procedures

Food and Drug Administration (FDA) regulations and National Cancer Institute (NCI) policy require all individuals contributing to NCI-sponsored trials to register and to renew their registration annually. To register, all individuals must obtain a Cancer Therapy Evaluation Program (CTEP) Identity and Access Management (IAM) account (https://ctepcore.nci.nih.gov/iam). In addition, persons with a registration type of Investigator (IVR), Non-Physician Investigator (NPIVR), or Associate Plus (AP) (i.e., clinical site staff requiring write access to OPEN, RAVE, or TRIAD or acting as a primary site contact) must complete their annual registration using CTEP's web-based Registration and Credential Repository (RCR) <https://ctepcore.nci.nih.gov/rcr >. Documentation requirements per registration type are outlined in the table below

Documentation Required	IVR	NPIVR	AP	A
FDA Form 1572	v	~		
Financial Disclosure Form	v	~	•	
NCI Biosketch (education, training, employment, license, and certification)	~	¥	¥	
HSP/GCP training	v	*	•	
Agent Shipment Form (if applicable)	~			
CV (optional)	v	•	~	

An active CTEP-IAM user account and appropriate RCR registration is required to access all CTEP and CTSU (Cancer Trials Support Unit) websites and applications. In addition, IVRs and NPIVRs must list all clinical practice sites and

IRBs covering their practice sites on the FDA Form 1572 in RCR to allow the following:

- Added to a site roster
- Assigned the treating, credit, consenting, or drug shipment (IVR only) tasks in OPEN
- Act as the site-protocol PI on the IRB approval
- Assigned the Clinical Investigator (CI) role on the Delegation of Tasks Log (DTL).

Additional information can be found on the CTEP website at < https://ctep.cancer.gov/investigatorResources/default.htm >. For questions, please contact the RCR Help Desk by email at < [contact] >.

b. CTEP Associate Registration Procedures

The Cancer Therapy Evaluation Program (CTEP) Identity and Access Management (IAM) application is a web-based application intended for use by both Investigators (i.e., all physicians involved in the conduct of NCI-sponsored clinical trials) and Associates (i.e., all staff involved in the conduct of NCI-sponsored clinical trials).

Associates will use the CTEP-IAM application to register (both initial registration and annual re-registration) with CTEP and to obtain a user account.

Investigators will use the CTEP-IAM application to obtain a user account only. (See CTEP Investigator Registration Procedures above for information on registering with CTEP as an Investigator, which must be completed before a CTEP-IAM account can be requested.)

An active CTEP-IAM user account will be needed to access all CTEP and CTSU (Cancer Trials Support Unit) websites and applications, including the CTSU members' website.

Additional information can be found on the CTEP website at http://ctep.cancer.gov/branches/pmb/associate registration.htm. For ques-tions, please contact the **CTEP Associate Registration Help Desk** by email at [contact].

c. CTSU Registration Procedures

This study is supported by the NCI Cancer Trials Support Unit (CTSU).

1. IRB Approval:

Each investigator or group of investigators at a clinical site must obtain IRB approval for this protocol and submit IRB approval and supporting documentation to the CTSU Regulatory Office before they can be approved to enroll patients. Assignment of site registration status in the CTSU Regulatory Support System (RSS) uses extensive data to make a determination of whether a site has fulfilled all regulatory criteria including but not limited to: an active Federal Wide Assurance (FWA) number, an active roster affiliation with the Lead Network or a participating organization, a valid IRB approval, and compliance with all protocol specific requirements.

Sites participating on the NCI CIRB initiative that are approved by the CIRB for this study are not required to submit IRB approval documentation to the CTSU Regulatory Office. For sites using the CIRB, IRB approval information is received from the CIRB and applied to the RSS in an automated process. Signatory Institutions must submit a Study Specific Worksheet for Local Context (SSW) to the CIRB via IRBManager to indicate their intent to open the study locally. The CIRB's approval of the SSW is then communicated to the CTSU Regulatory Office. In order for the SSW approval to be processed, the Signatory Institution must inform the CTSU which CIRB-approved institutions aligned with the Signatory Institution are participating in the study.

2. Downloading Site Registration Documents:

Site registration forms may be downloaded from the **S1702** protocol page located on the CTSU members' website.

- Go to https://www.ctsu.org and log in to the members' area using your CTEP-IAM username and password
- Click on the Protocols tab in the upper left of your screen
- Either enter the protocol # in the search field at the top of the protocol tree, or
- Click on the By Lead Organization folder to expand
- Click on the SWOG link to expand, then select trial protocol S1702 Click on LPO Documents, select the Site Registration documents link, and download and complete the forms provided.
- 3. Requirements For **S1702** Site Registration:
  - CTSU Transmittal Sheet (optional)
  - IRB approval (For sites not participating via the NCI CIRB; local IRB documentation, an IRB-signed CTSU IRB Certification Form, Protocol of Human Subjects Assurance Identification/IRB Certification/Declaration of Exemption Form, or combination is accepted)
- 4. Submitting Regulatory Documents:

Submit required forms and documents to the CTSU Regulatory Office, via the Regulatory Submission Portal, where they will be entered and tracked in the CTSU RSS.

Regulatory Submission Portal: www.ctsu.org (members' area) → Regulatory Tab → Regulatory Submission

When applicable original documents should be mailed to: CTSU Regulatory Office [name] Institutions with patients waiting that are unable to use the Portal should alert the CTSU Regulatory Office immediately at [name] in order to receive further instruction and support.

5. Checking Your Site's Registration Status:

You can verify your site registration status on the members' section of the CTSU website.

- Go to https://www.ctsu.org and log in to the members' area using your CTEP-IAM username and password
- Click on the Regulatory tab at the top of your screen
- Click on the Site Registration tab
- Enter your 5-character CTEP Institution Code and click on Go

Note: The status given only reflects compliance with IRB documentation and institutional compliance with protocol-specific requirements as outlined by the Lead Network. It does not reflect compliance with protocol requirements for individuals participating on the protocol or the enrolling investigator's status with the NCI or their affiliated networks.

13.3 OPEN Registration Requirements

The individual registering the patient must have completed the appropriate SWOG Registration Worksheet. The completed form must be referred to during the registration but should not be submitted as part of the patient data.

Patient enrollment will be facilitated using the Oncology Patient Enrollment Network (OPEN). OPEN is a web-based registration system available on a 24/7 basis. To access OPEN, the site user must have an active CTEP-IAM account (check at < https://eapps-ctep.nci.nih.gov/iam/index.jsp >) and a 'Registrar' role on either the LPO or participating organization roster.

OPEN will also ask additional questions that are not present on the SWOG Registration Worksheet. The individual registering the patient must be prepared to provide answers to the following questions:

- a. Institution CTEP ID
- b. Protocol Number
- c. Registration Step
- d. Treating Investigator
- e. Credit Investigator
- f. Patient Initials
- g. Patient's Date of Birth
- h. Patient SSN (SSN is desired, but optional. Do not enter invalid numbers.)
- i. Country of Residence
- j. ZIP Code
- k. Gender (select one):
  - Female Gender
  - Male Gender

- I. Ethnicity (select one):
  - Hispanic or Latino
  - Not Hispanic or Latino
  - Unknown
- m. Method of Payment (select one):
  - Private Insurance
  - Medicare
  - Medicare and Private Insurance
  - Medicaid
  - Medicaid and Medicare
  - Military or Veterans Sponsored NOS
  - Military Sponsored (Including Champus & Tricare)
  - Veterans Sponsored
  - Self Pay (No Insurance)
  - No Means of Payment (No Insurance)
  - Other
  - Unknown
- n. Race (select all that apply):
  - American Indian or Alaska Native
  - Asian
  - Black or African American
  - Native Hawaiian or other Pacific Islander
  - White
  - Unknown
- 13.4 Registration Procedures
  - a. All site staff will use OPEN to enroll patients to this study. OPEN is integrated with the CTSU Enterprise System for regulatory and roster data and, upon enrollment, initializes the patient in the Rave database. OPEN can be accessed at https://open.ctsu.org, from the OPEN tab on the CTSU members' side of the website at https://www.ctsu.org, or from the OPEN Patient Registration link on the SWOG CRA Workbench.
  - b. Prior to accessing OPEN site staff should verify the following:
    - All eligibility criteria have been met within the protocol stated timeframes and the affirmation of eligibility on the Registration Worksheet has been signed by the registering investigator or another investigator designate. Site staff should refer to Section 5.0 to verify eligibility.
    - All patients have signed an appropriate consent form and HIPAA authorization form (if applicable).
  - c. The OPEN system will provide the site with a printable confirmation of registration and treatment information. Please print this confirmation for your records.
  - d. Further instructional information is provided on the OPEN tab on the CTSU members' side of the website at https://www.ctsu.org or at https://open.ctsu.org. For any additional questions contact the CTSU Help Desk at [name] or [contact].

- 13.5 Exceptions to SWOG registration policies will not be permitted.
  - a. Patients must meet all eligibility requirements.
  - b. Institutions must be identified as approved for registration.
  - c. Registrations may not be cancelled.
  - d. Late registrations (after initiation of treatment) will not be accepted.

#### 14.0 DATA SUBMISSION SCHEDULE

14.1 Data Submission Requirement

Data must be submitted according to the protocol requirements for **ALL** patients registered, whether or not assigned treatment is administered, including patients deemed to be ineligible. Patients for whom documentation is inadequate to determine eligibility will generally be deemed ineligible

14.2 Master Forms

Master forms can be found on the protocol abstract page on the SWOG website www.swog.org and (with the exception of the sample consent form and the Registration Worksheet) must be submitted on-line via the Web; see Section 14.3a for details.

- 14.3 Data Submission Procedures
  - a. Data collection for this study will be done exclusively through the Medidata Rave® clinical data management system. Access to the trial in Rave is granted through the iMedidata application to all persons with the appropriate roles assigned in Regulatory Support System (RSS). To access Rave via iMedidata, you must have an active CTEP-IAM account (check at https://eapps-ctep.nci.nih.gov/iam/index.jsp) and the appropriate Rave role (Rave CRA, Read-Only, Site Investigator) on either the LPO or participating organization roster at the enrolling site.

Upon initial site registration approval for the study in RSS, all persons with Rave roles assigned on the appropriate roster will be sent a study invitation e-mail from iMedidata. To accept the invitation, site users must log into the Select Login https://login.imedidata.com/selectlogin using their CTEP-IAM user name and password, and click on the "accept" link in the upper right-corner of the iMedidata page. Please note, site users will not be able to access the study in Rave until all required Medidata and study specific trainings are completed. Trainings will be in the form of electronic learnings (eLearnings), and can be accessed by clicking on the link in the upper right pane of the iMedidata screen.

Users that have not previously activated their iMedidata/Rave account at the time of initial registration approval for the study in RSS will also receive a separate invitation from iMedidata to activate their account. Account activation instructions are located on the CTSU website, Rave tab under the Rave resource materials (Medidata Account Activation and Study Invitation Acceptance). Additional information on iMedidata/Rave is available on the CTSU members' website under the Rave tab at www.ctsu.org/RAVE/ or by contacting the CTSU help Desk at [name] or by e-mail at ctsu.org/activate.com.

b. You may also access Rave® via the SWOG CRA Workbench. Go to the SWOG web site http://swog.org and logon to the Members Area using your SWOG Roster ID Number and password. After you have logged on, click on *Workbenches*, then *CRA Workbench* to access the home page for the CRA Workbench and follow the link to Rave® provided in the left-hand navigation panel.

To access the CRA Workbench the following must be done (in order):

- 1. You are entered into the SWOG Roster and issued a SWOG Roster ID Number,
- 2. You are associated as an investigator or CRA/RN at the institution where the patient is being treated or followed,
- 3. Your Web User Administrator has added you as a web user and has given you the appropriate system permissions to view data for that institution.

For assistance with points 1 and 2 call the Operations Office at [name]. For point 3, contact your local Web User Administrator (refer to the "Who is my Web User Administrator?" function on the swog.org Members logon page).

14.4 Data Submission Overview and Timepoints

### a. WITHIN 7 DAYS OF REGISTRATION:

Submit the following:

Onstudy Form

AL Baseline Tumor Assessment Form

Pathology report, confirming AL amyloidosis (as defined in Section 5.1)

If organ involvement was assessed by biopsy, submit the pathology report documenting the involvement (see Section 5.1d).

If patient has involvement of the liver or lymph nodes, submit radiology reports (ultrasound, CT, or MRI) to assess liver and lymph node size at baseline.

See Section 15.0 for specimen submission requirements.

#### b. WITHIN 35 DAYS AFTER REGISTRATION:

Submit the following:

**S1702** Cytogenetics and FISH Analysis Form.

Institutional Flow Cytometry Report for Immunophenotyping and **S1702** Immunophenotyping Form

Institutional Cytogenetics Report, FISH Analysis Report, and Bone Marrow Aspirate and Biopsy Report

### c. WITHIN 14 DAYS AFTER EACH CYCLE OF TREATMENT:

Submit the following:

S1702 Treatment Form

**S1702** Adverse Event Form

AL Follow Up Tumor Assessment Form

d. WITHIN 30 DAYS OF DISCONTINUATION OF TREATMENT:

Submit the following:

Off Treatment Notice

S1702 Treatment Form

**S1702** Adverse Event Form

AL Follow Up Tumor Assessment Form

e. WITHIN 14 DAYS OF PROGRESSION/RELAPSE:

Submit the S1702 Treatment Form and S1702 Adverse Event Form (if the patient was still on protocol treatment),

Submit the AL Follow Up Tumor Assessment Form

#### f. EVERY 6 MONTHS FOR 4 YEARS AFTER REGISTRATION:

Submit the following:

Follow Up Form

Late Effects Form (if prior to treatment for progression or relapse or a second primary, and prior to non-protocol treatment, the patient experiences any severe [Grade  $\geq$  3] long term toxicity that has not been previously reported).

g. WITHIN 14 DAYS OF SECOND MALIGNANCY:

Submit the following:

Follow Up Form

h. WITHIN 4 WEEKS OF KNOWLEDGE OF DEATH:

Submit the Notice of Death **and a final** S1702 Treatment Form and S1702 Adverse Event (if the patient was still on protocol treatment) or Follow-Up Form (if the patient was off protocol treatment) documenting death information.

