### 1.0 OBJECTIVES

#### 1.1 Primary Objective

To assess the efficacy as measured by the confirmed overall hematologic response rate (partial response or better) of isatuximab in relapsed/ refractory systemic light chain (AL) amyloidosis.

- 1.2 Secondary Objectives
  - a. To evaluate toxicities in the treatment of relapsed/ refractory AL amyloidosis with isatuximab.
  - b. To evaluate time to hematologic response.
  - c. To evaluate duration of response.
  - d. To evaluate progression-free survival (PFS).
  - e. To evaluate overall survival (OS).
- 1.3 Other Objectives
  - a. To evaluate efficacy of isatuximab in relapsed/ refractory immunoglobulin amyloid light chain (AL) amyloidosis as measured by organ specific response rates (cardiac, renal, GI, liver, soft tissue, nerve), in the subset of patients that can be evaluated for organ response.
  - b. To evaluate time to organ response in the subset of patients that can be evaluated for organ response.

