#### Footnotes for Calendar 9 (Isatuximab)

- A Tests are to be performed per Section 5.1d for suspected organ involvement. If baseline test was performed and abnormality present, the tests will be repeat until off tx prior to progression.
- B See Section 15.1.
- c Prior to treatment on each day of isatuximab, or within 3 days prior to each administration.
- E See Section 7.1c for type and screen requirements. See Appendix 18.6 for sample type and screen card.
- F For women of childbearing potential, prior to beginning treatment at each cycle (or up to 3 days prior to Day 1).
- G If required: Day 1 of Cycles 1, 4, and 7, then every 3 cycles (+/- 7 days) during treatment, then every 6 months (+/- 21 days) hematologic progression.
- H If required: Day 1 of Cycles 1, 3, 5, then every 2 cycles (+/- 7 days) until completion of treatment, then every 6 months (+/- 21 days) until hematologic progression.
-  If required: Every 6 months during and after treatment until hematologic progression, then as clinically indicated.
- J TSH with reflex to free T4, and free T3 uric acid and LDH are required only when clinically indicated; however, baseline testing is encouraged to assess for thyroid involvement, if suspected.
- K See Section 7.4 for a detailed description of organ evaluation and 24 hour urine collection assessment criteria, including serum chemistry panel requirements. All evaluations will continue at specified intervals until one of the criteria for removal from protocol treatment has been met (see Section 7.5).
- L If required: Day 1 (+/- 3 days) of each cycle.
- M See treatment plan Section 7.3.
- N See Sections 5.1d.5 and 7.1b.
- o Must include assessment of soft tissue and lymph nodes, if present at baseline; see Section 7.4e.
- P May be either INR or PT and PTT. Whichever is performed at baseline should be used throughout treatment.
- Q Assessments should continue until resolution of all acute adverse events.
- R Only required per Section 5.3 Eligibility.

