#### 10.0 CRITERIA FOR EVALUATION AND ENDPOINT ANALYSIS

10.1 Measurable disease

For the purpose of measuring hematologic response, measurable disease is defined as:

a. Positive monoclonal serum immunofixation electrophoresis or urine immunofixation electrophoresis,

and/or

- b. Serum free light chain ratio outside of normal range (normal range: 0.25 1.65)
- 10.2 Hematologic Response and Progression

Confirmation must be made by verification on two consecutive determinations.

- a. Hematologic response: (16, 17)
  - Complete Response (CR): CR is defined as laboratory values within the normal range free light chain (FLC) ratio (0.25 – 1.65) and negative serum and urine immunofixation (as per institutional laboratory values).
  - Very Good Partial Response (VGPR): A VGPR is defined as the difference between involved and uninvolved FLCs [dFLC] < 4.0 mg/dL.

  - Partial Response (PR): Partial Response is defined as a dFLC decrease of ≥ 50%, but remaining > 4.0 mg/dL
- b. Hematologic progression: 50% increase from nadir, or from baseline (if there was no response) in any ONE OR MORE of the following: *(18)* 
  - 1. Serum M-protein: 50% increase in Serum M protein to a value greater than 0.5 g/dL.
  - 2. Urine M protein: 50% increase in Urine M protein to a value greater than 200 mg/day (a visible peak must be present)
  - 3. Free light chain increase of 50% to a value greater than 10 mg/dL
- c. Stable Disease: Patients who do not meet criteria for objective response or progression (see Sections 10.2a and 10.2b) will be termed to have stable disease.
- 10.3 Organ Response (19)

Response to therapy in terms of improvement in organ dysfunction will be defined based on functional improvement in one or more involved organ systems. Only 1 parameter is required to satisfy the organ response criteria. In order to be classified as a confirmed organ response, confirmation must be made by verification on a second consecutive assessment at least 4 weeks after the first observation of response.

- a. Liver response requires either:
  - 1. A 50% decrease in (or normalization of, <1.5 IULN) alkaline phosphatase level, or
  - 2. A reduction in the span of the liver by at least 2 cm by radiographic determination.
- b. Renal response is defined as either: (20)
  - 1. A 30% decrease in urine total albumin; or

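### Section 14.4 schedules no disease-assessment form for patients off treatment and not yet progressed, although the calendar orders organ and light-chain tests in that period

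*Combined protocol and SAP*

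**What the plan says.** **Data submission (Section 14.4).** The AL Follow Up Tumor Assessment Form is due at three points: 14.4c, "WITHIN 14 DAYS AFTER EACH CYCLE OF TREATMENT"; 14.4d, "WITHIN 30 DAYS OF DISCONTINUATION OF TREATMENT"; and 14.4e, at progression or relapse, "Submit the AL Follow Up Tumor Assessment Form". Section 14.4f, "EVERY 6 MONTHS FOR 4 YEARS AFTER REGISTRATION", lists a Follow Up Form and, under conditions, a Late Effects Form. It does not list the AL form.

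**Calendar (Section 9.0).** The off-treatment, pre-progression column marks SPEP, free light chains, troponin, NT-proBNP, NYHA class, 24-hour urine, fecal fat, echocardiogram, imaging, and neurologic and GI evaluations. Footnote H, for example, runs its tests "until completion of treatment, then every 6 months (+/- 21 days) until hematologic progression".

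**Endpoint.** Objective 1.3a is the organ-specific response rate. Objective 1.3b is "To evaluate time to organ response in the subset of patients that can be evaluated for organ response". For a confirmed organ response, Section 10.3 says "confirmation must be made by verification on a second consecutive assessment at least 4 weeks after the first observation of response". Section 11.4 counts patients with documented organ response and does not limit this to the treatment period.

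**Form content.** The case report forms are not reproduced. Section 14.2 says "Master forms can be found on the protocol abstract page on the SWOG website".

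**The concern.** The calendar and the data schedule do not match. Endpoint tests are ordered for a period in which the form designed for disease assessments is not due. A patient who stops without progression, and never progresses, has no AL form scheduled after the discontinuation form.

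The gap is selective. A patient who progresses later triggers another AL form; a durable non-progressor does not. Patients who stop early spend more of their follow-up in the uncovered period than those who complete 24 cycles. If off-treatment results are not collected elsewhere, the organ response rate and time to organ response would partly reflect how long a patient stayed on treatment, and not only what happened to the organ.

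**Working it through.** **1. The plan's own figures.** The plan gives no figure on this point. Its design figures are a significance level of 2% and power of 87%. With stage 1 of 20 patients (continue on at least 2 responses) and success at 8 or more of 35, the chance of success is the sum over x ≥ 2 of P(Bin(20, p) = x) × P(Bin(15, p) ≥ 8 − x). This gives 1.99% at p = 0.10 and 86.6% at p = 0.30, so both figures reproduce. They concern hematologic response only.

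**2. Forms against tests.**

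| Period | Tests in calendar 9.0 | AL form in 14.4 |
|---|---|---|
| On treatment | each cycle, or every 2 or 3 cycles, or 6-monthly | after each cycle (14.4c) |
| Stopping | – | once, within 30 days (14.4d) |
| Off treatment, not progressed | light chains, SPEP, organ tests | none listed (14.4f) |
| Progression | – | within 14 days (14.4e) |

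**3. Size of the uncovered window.** Inputs are a 28-day cycle and a maximum of 24 cycles (7.3), and follow-up to 4 years from registration (7.7), taken as 4 × 365.25 = 1,461 days. Six months is 182.6 days. Treatment is assumed to start at registration without delays.

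- 24 cycles: 24 × 28 = 672 days; 1,461 − 672 = 789; 789 / 182.6 = 4.3, so at most 4 evaluations.
- 12 cycles: 336 days; 1,125 / 182.6 = 6.2, so at most 6.
- 4 cycles: 112 days; 1,349 / 182.6 = 7.4, so at most 7.

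These are maxima. They require the patient to be alive and free of hematologic progression to year 4, and they read footnotes G to I as the governing schedule.

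**4. Where confirmation falls, for a patient completing 24 cycles.**

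- Fecal fat (footnote G): Cycles 1, 4, 7, then every 3, so the last on-treatment test is Cycle 22. The next would be Cycle 25, which does not exist. A response first seen at Cycle 22 is therefore confirmed at a 6-monthly off-treatment test.
- Liver span (footnote I): 6-monthly. If a reduction is first seen at month 18, the next scan is at month 24, or day 730.5. That is 730.5 − 672 = 58.5 days after Cycle 24 ends. Even at the early edge of the 21-day window it is 37.5 days after, later than the 30-day form.

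For patients who stop mid-course the same happens earlier. With 6-monthly imaging, a reduction seen at month 6 in a patient who stops before month 12 can be confirmed by span only off treatment.

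**5. Is the off-treatment testing itself certain?** Not for every test. Footnote K ends the evaluations it marks at removal from protocol treatment. Echocardiogram carries both G and K; 24-hour urine and the peripheral neurologic and GI evaluations carry both H and K. For these the footnotes conflict. Footnote L gives NT-proBNP and troponin a per-cycle schedule and no off-treatment interval, although the column marks them. K does not mark light chains, SPEP, NT-proBNP, troponin, imaging, fecal fat or the autonomic evaluation, so the gap remains for these whichever way K is resolved.

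**The case against.** **The Follow Up Form may already collect these results.** It is due every 6 months for 4 years and its fields are not shown. The form due at progression might also carry earlier results. This stands. A reader might infer that no form carries off-treatment assessments and that these responses never reach the analysis; the documents do not support that. Use of the Follow Up Form for second malignancy and death (14.4g-h) suggests a general status form but does not prove it.

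**Confirmation may not be needed.** Section 11.4 speaks of documented, not confirmed, organ response, so a response reported on the last on-treatment form may already count. This stands as an ambiguity between 10.3 and 11.4. It does not help responses first seen off treatment.

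**Few patients may be affected.** In the myeloma data in Section 2.4, most who stopped did so for progression: 69 of 81 (85%) and 73 of 85 (86%), with 4 and 7 stopping for adverse events. Patients who stop for hematologic progression have no pre-progression off-treatment tests to lose. This is fair, but it is a different disease, and here treatment also ends at 24 cycles, so completers enter the uncovered period too.

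**The primary endpoint.** Because off-treatment light chains share the gap, a reader might infer lost hematologic responses and reduced power. The documents do not show this. Light chains are measured every cycle, the AL form is due every cycle and again at discontinuation, and Section 10.2 asks for two consecutive determinations with no minimum interval. Loss would require a first or confirming result after the discontinuation form in a patient who has not progressed, and no figure in the documents gives a rate for that.

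**Conclusion.** The mismatch is real on the face of the protocol. Calendar 9.0 orders assessments off treatment before progression, and 14.4 schedules no AL form between the one due within 30 days of discontinuation and the one due at progression. Whether data are lost depends on one unseen fact, the content of the Follow Up Form. If it does not duplicate the AL form, organ responses first seen or confirmed off treatment may be missed in patients who stop without progression, and objectives 1.3a-b become dependent on treatment duration.

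The exposure is at most 4 six-monthly evaluations after full treatment and at most 7 after stopping at Cycle 4. The documents give no rate of off-treatment organ response, so no number of missed responses can be stated. Organ response is a descriptive other objective and plays no part in the 8-of-35 rule. The correction is worth making because it is cheap and the tests are already ordered.

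**What to change.** 1. **Section 14.4f:** add the AL Follow Up Tumor Assessment Form every 6 months for patients off protocol treatment, until hematologic progression or start of non-protocol therapy, reporting all disease assessments since the last form. If the Follow Up Form already captures these results, saying so in 14.4f would close the data gap.
2. **Section 11.4:** state that organ response uses assessments up to the earlier of hematologic progression or start of non-protocol therapy, and whether it must be confirmed as in 10.3. The second cut-off matters: without it, a response to a later regimen could be credited to isatuximab.
3. **Section 9.0:** reconcile footnote K with footnotes G and H, so that it is clear which evaluations continue after treatment ends.

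Cost: one existing form every 6 months for these patients. Items 1 and 2 add no test or visit beyond those the calendar already marks. Item 3 requires the sponsor to settle which of the conflicting footnotes governs.
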